## 4. Methods

### 4.1 Participants

An *a priori* power analysis (G\*Power v. 3.1.5.1) indicated that 48 participants are required. This calculation is based on a small effect size (Cohen's  $f = 0.25$ ), an alpha level of .05, and a  $\beta$ -value of 0.8 for a repeated measures, within-between analysis of variance (ANOVA) design. Males (18-30 years of age) who have been performing structured resistance training ( $> 3x/week$  for  $\geq 6$  months) prior to the start of the study will be recruited. Resistance trained participants are being recruited to help reduce the influence that neuromuscular learning has on changes in muscle mass and muscle performance over time. Prior to the start of supplementation and training, participants will fill out a questionnaire which assesses their readiness for participation in resistance training. Participants will also fill out a leisure time exercise questionnaire, which indicates the average number of times that strenuous (i.e. heart beats rapidly), moderate (i.e. not exhausting), and mild exercise (i.e. minimal effort) is performed per week. Participants will be excluded from the study if they have taken medications that affect muscle biology or creatine monohydrate  $\leq 12$  weeks prior to the start of resistance training and supplementation; if they have diseases that are known to affect muscle biology (i.e. Crohn's Disease), if they have pre-existing kidney or liver abnormalities, or if they plan to travel  $\geq 1$  week during the study where they have no access to a fitness facility. Habitual caffeine consumers are being included because regular caffeine consumption does not negate the beneficial effects of caffeine supplementation. Furthermore, habitual caffeine consumers who withdraw from caffeine may experience adverse symptoms which could negatively affect exercise performance. Participants will be instructed not to change their habitual diet or engage in additional physical activity that is not part of their normal daily routine or consume non-steroidal anti-inflammatory drugs during resistance training and

supplementation, as these interventions can affect muscle protein synthesis. The study will be approved by the Research Ethics Board at the University of Regina. Participants will be informed of the risks and purposes of the study before written consent is obtained.

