#### **4.2 Research Design**[L][SEP]

The study will be a double-blind, repeated measures design. In order to minimize group differences, participants will be matched according to age and weight and be randomized on a 1:1:1:1 basis to one of four groups: Creatine + Caffeine (CR-CAF; 0.1 g/kg of creatine monohydrate powder + 3 mg/kg of caffeine [micronized powder]); Creatine (CR; 0.1 g/kg of creatine monohydrate powder + 3 mg/kg of caffeine placebo [micronized cellulose powder]), Caffeine (CAF; 3 mg/kg of caffeine + 0.1 g/kg of creatine monohydrate placebo [maltodextrin]) or placebo (PLA; 0.1g/kg creatine monohydrate placebo + 3 mg/kg of caffeine placebo). An individual, blinded to supplement and group allocation, will be responsible for the preparation of study kits. Each study kit will contain the participants supplement for the duration of the study, detailed supplementation instructions, measuring spoons, supplementation compliance log, daily caffeine consumption log and a resistance training log. Supplement powders will be similar in energy content, color, taste, texture, and appearance. The creatine dosage of 0.1 g/kg has previously been shown to be effective for increasing muscle mass and muscle performance. The caffeine dosage of 3 mg/kg has been shown to increase muscle performance. Participants will be instructed to refrain from additional caffeine sources  $\geq 3$  hour prior to consuming their supplement so that a valid estimate regarding the effects of caffeine supplementation on muscle can be made. On training days, participants will mix their supplement powder in water and consume the solution 60 minutes prior to exercise. Sixty minutes was chosen because this is the approximate time it takes for peak plasma caffeine concentrations to occur after caffeine ingestion and pre-exercise

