#### 4.5 Statistical Analysis

A 4 (group: CR-CAF vs. CR vs. CAF vs. PLA) x 2 (time: pre- vs. post- training) repeated measures analysis of variance (ANOVA) will be used to determine differences between groups over time for the dependent variables of muscle thickness, muscle strength, muscle endurance and diet. If significant interactions are detected, a one-factor ANOVA on absolute change scores ( $\Delta = \text{post mean} - \text{pre mean}$ ) will be performed to confirm the interaction. A one-factor ANOVA will be used to assess baseline data and training volume. Significance is set *a priori* at an alpha level of  $p < 0.05$ . Cohen's *d* effect size (ES) for significant main effects and interactions will be calculated as  $\text{post-training mean} - \text{pre-training mean} / \text{pooled pre-training standard deviation mean}$  (Cohen, 1992). An ES of 0.00-0.19 is considered trivial, 0.20-0.49 is considered small, 0.50-0.79 is considered moderate, and  $\geq 0.80$  is considered large (Cohen, 1992). Statistical analyses will be performed using IBM® SPSS® Statistics, v. 24.

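### Section 4.1 misstates the basis for 48 participants: the 0.8 is power, not beta, and f = 0.25 should not be called small

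*Protocol*

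**What the plan says.** Protocol section 4.1 reports a G\*Power calculation that "indicated that 48 participants are required". It continues "This calculation is based on a small effect size", gives Cohen's f = 0.25 and "an alpha level of .05", and then states a beta-"value of 0.8 for a repeated measures, within-between analysis of variance (ANOVA) design". It gives no pre-post correlation and does not say which effect in the ANOVA was powered.

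The rest of the design is fixed elsewhere. Section 4.2 has participants "randomized on a 1:1:1:1 basis to one of four groups". Section 4.5 sets out a 4 (group) by 2 (time) repeated measures ANOVA that "will be used to determine differences between groups over time for the dependent variables". The test that answers the trial's question is therefore the group-by-time interaction. If it is significant, it is followed by "a one-factor ANOVA on absolute change scores".

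Section 4.5 also grades Cohen's d, defined as the pre-to-post change over the pooled pre-training SD: "0.20-0.49 is considered small, 0.50-0.79 is considered moderate", and large from 0.80.

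**The concern.** Beta is the type II error rate, so a beta of 0.8 means that a true effect of the assumed size would be missed four times in five. That is a wrong statement of the operating characteristic in the sentence that justifies the sample size.

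The word small is a separate problem. It tells the reader that 48 participants were chosen to detect a small effect. If f = 0.25 is in fact a sizeable difference between groups in their change, a non-significant interaction could later be taken as evidence against small effects of creatine or caffeine. The calculation would not support that reading.

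**Working it through.** **Inputs.** From section 4.1: N = 48, f = 0.25, alpha 0.05. From sections 4.2 and 4.5: k = 4 equal groups (12 each) and m = 2 time points. Assumed, because the protocol does not give it: the pre-post correlation rho.

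**Step 1: reproduce the 48.** For the group-by-time interaction, the noncentrality is lambda = f² × N × m / (1 − rho), with df1 = (k − 1)(m − 1) = 3 and df2 = (N − k)(m − 1) = N − 4.
- At rho = 0.5 and N = 48: lambda = 0.0625 × 48 × 2 / 0.5 = 12.0, df = (3, 44), power **0.803**.
- At rho = 0.5 and N = 44: lambda = 11.0, df = (3, 40), power **0.760**.

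In steps of four (equal groups), 48 is the smallest N that reaches 0.80. This holds for rho from about 0.50 to 0.54. At rho = 0.5 the other effects in this ANOVA do not give 48: the time main effect needs 36 and the group main effect 136.

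**Step 2: take beta = 0.8 literally (power 0.20).** The same formula with f = 0.25 gives:

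| rho | 0 | 0.1–0.2 | 0.3–0.5 | 0.7 | 0.9 |
|---|---|---|---|---|---|
| N needed | 24 | 20 | 16 | 12 | 8 |

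No correlation in this range leads to 48. The printed sample size fits power 0.80, that is beta 0.20.

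**Step 3: what f = 0.25 means for the interaction.** With two time points, the interaction effect in each cell is plus or minus half of the group's deviation from the average change. Hence f² = Var(group mean changes) / (4 sigma²), where sigma is the common pre and post SD. The SD of the four mean changes is then 2 × 0.25 × sigma = 0.5 sigma. Let d be the largest difference in change between any two groups, in units of sigma.

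| Pattern of the four mean changes | Variance of mean changes | d when their SD is 0.5 |
|---|---|---|
| Two groups against two | d²/4 | 1.00 |
| One group against three | 3d²/16 | 1.15 |
| Two extremes, two midway | d²/8 | 1.41 |

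This range does not depend on rho. A simulation with 12 per group and rho = 0.5 gave power 0.798 for the first pattern and 0.807 for the third.

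**Step 4: the most lenient reading.** The two-group conversion d = 2f gives 2 × 0.25 = 0.50. The small band in section 4.5 ends at 0.49.

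**Step 5: what 48 participants detect.** This is a different quantity from step 3 and does depend on rho. Largest difference in change detectable with 80% power, over the three patterns:

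| rho | 0.3 | 0.5 | 0.7 | 0.8 | 0.9 |
|---|---|---|---|---|---|
| d (SD) | 1.18–1.67 | 1.00–1.41 | 0.77–1.09 | 0.63–0.89 | 0.45–0.63 |

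Power at N = 48 on the lenient scale of step 4, for both ends of the small band:

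| rho | 0.5 | 0.7 | 0.8 | 0.9 |
|---|---|---|---|---|
| d = 0.20 (f = 0.10) | 0.17 | 0.27 | 0.39 | 0.70 |
| d = 0.49 (f = 0.245) | 0.785 | 0.954 | 0.995 | above 0.99 |

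**The case against.** The strongest reply is that nothing in the arithmetic is wrong. The 48 reproduces, and most readers will recognise 0.8 as power. That stands, and it limits the point to the description of the calculation. A reader might infer from the printed beta that the trial has only 20% power. The protocol's own 48 rules that out, since no correlation between 0 and 0.9 leads there from 20% power.

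The second reply concerns small. The protocol offers no scale for f, and the bands in section 4.5 grade a pre-to-post change, not a difference between groups in change. Both comparisons, 1.0–1.4 SD and d = 0.50, borrow those bands and are approximate. On the lenient scale the miss is slight: 0.50 against 0.49, with power still 0.785 at the top of the band when rho is 0.5. This also stands. It does not rescue the label, because neither reading places f = 0.25 inside the small band and the interaction reading places it far outside.

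Third, a reader might infer that 48 participants can detect only differences of 1.0–1.4 SD, or that the trial is too small. The documents do not support either. The 1.0–1.4 SD range is what f = 0.25 implies. What 48 participants detect coincides with it only near rho = 0.5 and is smaller at higher correlations. The protocol states no correlation, so no shortfall can be shown.

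Last, nothing in section 4.5 commits the investigators to reading a null result as excluding small effects. That harm is possible, not planned.

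**Conclusion.** The point holds as an error of description in section 4.1. It should be corrected, but it does not affect the sample size or the analysis.

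- The beta of 0.8 is wrong as printed. The 48 corresponds to power 0.80 (beta 0.20), on the assumption that the interaction was powered with a pre-post correlation of about 0.5.
- Small does not fit f = 0.25. For the interaction it implies a largest between-group difference in change of about 1.0–1.4 pre-training SD, assuming equal pre and post SDs. The lenient conversion misses the small band only narrowly, and the use of that band is approximate in both cases.
- The difference that 48 participants can detect cannot be fixed from the protocol, because it turns on the unstated correlation.

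The mislabelled beta is certain. The objection to small is well supported, but it rests on a conversion between effect-size scales.

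**What to change.** Keep N = 48 and the analysis of section 4.5. Replace the sentence in section 4.1 with wording along these lines: *The sample size is for the group-by-time interaction in a repeated measures, within-between ANOVA, with Cohen's f = 0.25, alpha .05, power 0.80 (beta 0.20) and a pre-post correlation of [the value the sponsor entered].* Leave out the word small.

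If the sponsor wants to express the effect in SD units, the text should say that f = 0.25 implies a largest between-group difference in change of about 1.0–1.4 pre-training SD, depending on the pattern of the four means and assuming equal pre and post SDs. That addition is optional. It should not be presented as the smallest difference the trial can detect unless the correlation is given with it.

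The cost is one sentence, with no extra participants. The one drawback for the sponsor is that the stated property looks slightly less favourable, because the trial can no longer be described as sized for a small effect.

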#### **4.2 Research Design**[L][SEP]

The study will be a double-blind, repeated measures design. In order to minimize group differences, participants will be matched according to age and weight and be randomized on a 1:1:1:1 basis to one of four groups: Creatine + Caffeine (CR-CAF; 0.1 g/kg of creatine monohydrate powder + 3 mg/kg of caffeine [micronized powder]); Creatine (CR; 0.1 g/kg of creatine monohydrate powder + 3 mg/kg of caffeine placebo [micronized cellulose powder]), Caffeine (CAF; 3 mg/kg of caffeine + 0.1 g/kg of creatine monohydrate placebo [maltodextrin]) or placebo (PLA; 0.1g/kg creatine monohydrate placebo + 3 mg/kg of caffeine placebo). An individual, blinded to supplement and group allocation, will be responsible for the preparation of study kits. Each study kit will contain the participants supplement for the duration of the study, detailed supplementation instructions, measuring spoons, supplementation compliance log, daily caffeine consumption log and a resistance training log. Supplement powders will be similar in energy content, color, taste, texture, and appearance. The creatine dosage of 0.1 g/kg has previously been shown to be effective for increasing muscle mass and muscle performance. The caffeine dosage of 3 mg/kg has been shown to increase muscle performance. Participants will be instructed to refrain from additional caffeine sources  $\geq 3$  hour prior to consuming their supplement so that a valid estimate regarding the effects of caffeine supplementation on muscle can be made. On training days, participants will mix their supplement powder in water and consume the solution 60 minutes prior to exercise. Sixty minutes was chosen because this is the approximate time it takes for peak plasma caffeine concentrations to occur after caffeine ingestion and pre-exercise

creatine supplementation has a beneficial effect on muscle performance. On non-training days, participants will refrain from consuming their supplement as the purpose of the study is to investigate the effects of pre-exercise creatine and caffeine co-supplementation. Adherence with the supplementation protocol will be assessed using compliance logs. Habitual daily caffeine consumption will be recorded using caffeine logs. Upon completion of the study, participants will be asked whether they thought they were administered creatine and caffeine, creatine, placebo, or unsure about what supplement they consumed. The primary dependent variables that will be measured at baseline and after the intervention include: (1) muscle thickness (elbow and knee flexors and extensors; ultrasonography), (2) muscle strength (1-RM leg press, chest press) and (3) muscle endurance (leg press and chest press; maximum number of repetitions performed for 1 set using 50% baseline 1-RM). In addition, participants will fill out a 3-day food diary during the first and final week of supplementation and training to determine whether total energy (kcal) and macronutrient intake changed over time.

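### Randomisation is matched on age and weight, but no planned analysis uses either variable: the tests stay valid but are somewhat conservative, and prespecified adjustment is a nearly free improvement

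*Protocol*

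**What the plan says.** Protocol section 4.2 restricts the allocation: "participants will be matched according to age and weight and be randomized on a 1:1:1:1 basis to one of four groups". The stated aim is "In order to minimize group differences". It does not say how the matching is carried out, for example whether formal sets of four are built.

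Protocol section 4.5 names the analyses:

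- The main model is "A 4 (group: CR-CAF vs. CR vs. CAF vs. PLA) x 2 (time: pre- vs. post- training) repeated measures analysis of variance (ANOVA"), applied to muscle thickness, strength, endurance and diet.
- A significant interaction is followed by "a one-factor ANOVA on absolute change scores".
- For the remaining comparisons, "A one-factor ANOVA will be used to assess baseline data and training volume".

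Group and time are the only factors in any of these. Section 4.1 sizes the trial for the same kind of model: the calculation "indicated that 48 participants are required", with a "value of 0.8 for a repeated measures, within-between analysis of variance (ANOVA) design".

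**The concern.** When allocation is restricted on variables that predict the outcome, the arms differ less by chance on those variables than under simple randomisation. The true sampling variance of the arm contrasts falls. An analysis that omits the variables estimates its error from the full spread of participants within each arm, which still includes the part due to age and weight. The error term is then too large for the contrasts being tested and the F test rejects too rarely.

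What is at stake is efficiency. There are 12 men per arm and the stated sample size gives power only just above 0.80, so a missed effect is the main risk and there is little slack. Age and weight are already known for every participant, since the trial matches on both and doses by body weight.

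**Working it through.** **1. Reproduce the plan's figure.** From section 4.1: f = 0.25, alpha = 0.05, target power 0.8, N = 48. From section 4.5: k = 4 groups, m = 2 times. The pre–post correlation is not given; ρ = 0.5 and sphericity are assumed.

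λ = f²·N·m/(1 − ρ) = 0.0625 × 48 × 2 / 0.5 = 12, on (k − 1)(m − 1) = 3 and (N − k)(m − 1) = 44 degrees of freedom. The critical F is 2.82. Power is 0.803 at N = 48 and 0.760 at N = 44, so 48 reproduces.

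**2. Reduce the test to change scores.** With two time points, the group-by-time F equals the one-factor ANOVA F on post minus pre. Each man's own baseline therefore already removes stable effects of age and weight on the level of the outcome. What counts for this test is R², the share of variance in the *change* that the two variables explain. The protocol gives no figure, so a range is shown.

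**3. Size of the planned test.** With close matching, the between-arm mean square has expectation of about (1 − R²)σ² under the null, while the residual mean square stays near σ². In simulation at R² = 0.10 the residual mean square was 1.01 when the matching was ignored and 0.90 when it was used. Hence

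true size ≈ P(F(3, 44) > 2.816/(1 − R²)).

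At R² = 0.10 the threshold is 2.816/0.90 = 3.13, which gives 3.5%.

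**4. Power with adjustment.** Adjustment reduces the residual variance to (1 − R²)σ², so λ becomes about 12/(1 − R²) on 3 and 42 degrees of freedom. At R² = 0.10, λ = 13.3 and power is 0.845.

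**5. Simulation.** 48 men were placed in 12 matched sets of four, permuted 1:1:1:1 within sets, with an effect that the planned test detects with power of about 0.80. Runs with one matching index and with two separate matching variables agree closely:

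| R² (assumed) | Size by step 3 | Simulated size, planned test | Power, planned test | Power, adjusted |
|---|---|---|---|---|
| 0 | 5.0% | about 5% | 0.80 | 0.79–0.80 |
| 0.05 | 4.2% | 4.1–4.8% | 0.80 | 0.81–0.82 |
| 0.10 | 3.5% | 3.5–3.6% | 0.80 | 0.83–0.84 |
| 0.20 | 2.3% | 2.1–2.5% | 0.80–0.81 | 0.88–0.89 |
| 0.30 | 1.3% | 1.2–1.5% | 0.80–0.81 | 0.92–0.93 |

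The adjusted test holds its size at about 5% throughout. At R² = 0.02 adjustment makes almost no difference.

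**6. How much of the gain comes from the matching?** Without any matching, adjustment raises power from 0.804 to 0.824 at R² = 0.10 and from 0.796 to 0.868 at R² = 0.20. With matching it goes from 0.802 to 0.835 and from 0.807 to 0.884. The adjusted power is higher with matching by 0.835 − 0.824 = 0.011 and 0.884 − 0.868 = 0.016. Most of the gain is therefore what covariate adjustment gives in any trial.

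**7. Looser matching.** If men are matched on a joint index but only weight predicts change, the true size is 4.4% and 3.4% at R² = 0.10 and 0.20. If they are matched within enrolment cohorts of 12, it is 4.6% and 3.9%. Both lie closer to 5% than the table.

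**8. Training volume.** This is compared between arms as a level, with no baseline measurement. Step 2 gives it no protection, so the relevant R² is that of age and weight with the level itself and may be larger.

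**The case against.** The strongest reply is that nothing promised is lost. Section 4.1 sizes the trial for an unadjusted ANOVA, and the planned test keeps about 0.80 power at every R² tried. The matching also still does what section 4.2 says it is for: the arms are balanced and the estimates benefit. All of this stands.

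A second reply is that age and weight may hardly predict six-week change in resistance-trained men aged 18–30. This also stands as a possibility: at R² of 0.05 or less the gain is at most about two points of power. The eligibility criteria restrict age but not weight, however, and both variables were thought important enough to match on.

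A third reply is that covariates can be left to a statistical analysis plan. In part this stands, since section 4.5 does not forbid them. But it does name the model and its factors, and that model does not reflect the allocation. If a separate plan already adds age and weight, the two documents only need to agree.

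Several stronger conclusions are tempting, and the protocol does not support them:

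- A reader might infer that the tests are invalid or the type I error inflated. The error runs the other way.
- A reader might infer that 48 is too few or the power claim false. It reproduces, given ρ = 0.5.
- A reader might infer that the whole benefit of matching is thrown away. The balance is kept, and step 6 shows that matching accounts for only a point or so of adjusted power.
- A reader might infer that confidence intervals will be too wide. Section 4.5 plans none.
- A reader might tie the baseline one-factor ANOVA to this point. Whether to keep that test is a separate question.

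**Conclusion.** The design and the analysis do not match: age and weight govern the allocation in 4.2 and appear in no analysis in 4.5. The consequence is conditional and in the safe direction. If the two variables explain 10% of change-score variance and matching is close, the nominal 5% test runs at about 3.5%, and adjustment would lift power by three to four points. At 20% the figures are about 2.5% and about eight points. At 2% or less the effect is negligible. These sizes rest on an assumed R² and on close matching in sets of four, neither of which the protocol states; looser matching shrinks the conservatism. The point is a cheap efficiency improvement of low severity. It does not challenge the validity of the trial or its sample size.

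**What to change.** Add one sentence to section 4.5: age and body weight at baseline, continuous and mean-centred, are included as covariates in the group-by-time model for each outcome, with their interactions with time, and in the one-factor ANOVAs of change scores and of training volume.

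The covariate-by-time terms matter. Age and weight entered only as between-subject main effects would leave the group-by-time test unchanged. Entering both in the change-score ANOVA is equivalent.

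A factor for the matched set is possible if formal sets of four are built and recorded. It uses 12 − 1 = 11 degrees of freedom and recovers slightly less (0.831 against 0.844 at R² = 0.10), so the two covariates are preferable.

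The cost is two of 44 residual degrees of freedom, leaving 42. That is about one point of power or less if neither variable predicts the outcome. No new data, participants or procedures are needed, and naming the covariates now removes any later choice made after seeing the data.

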#### **4.3 Resistance Training Program**

Participants will follow the same periodized, resistance training program for 6 weeks. The program will consist of three sets of 6, 8, 10 repetitions to muscle fatigue in order. Resistance training will start on the first day of supplementation and will consist of a split routine involving whole body musculature. Day 1 will involve chest and biceps musculature and include the following exercises in order: machine-based chest press, free weight incline bench press or dumbbell press, free-weight flat dumbbell press, machine-based pec-dec, free-weight standing barbell curl, free-weight alternate arm dumbbell curl and machine-based preacher curl. Day 2 will involve leg and core musculature and include the following exercises in order: free-weight squat, machine-based leg press, machine-based leg extension, machine-based leg curl, machine-based calf raise, and

machine-based weighted abdominal crunches. Day 3 will serve as a rest day from training. Day 4 will involve back and triceps musculature and include the following exercises in order: body weight or weight-assisted chin-ups, machine-based seated row, machine-based lat pull-down, free-weight alternate dumb-bell row, free-weight close-grip bench press, machine-based cable triceps bar extension, and machine-based cable triceps rope extension. Day 5 will involve shoulder and core musculature and include the following exercises in order: free-weight dumbbell press, free-weight upright row, free-weight shrugs, free-weight or machine based lateral deltoid flys, free-weight or machine-based rear deltoid flys and machine-based weighted abdominal crunches. Day 6 will serve as a rest day from training. This cycle will be repeated for 6 weeks. Participants will maintain training logs to ensure adherence and compliance to the study and to determine total training volume (load x repetitions x sets).

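### The exit question on supplement guess offers answers for three of the four arms and omits caffeine alone, so the check of blinding is incomplete

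*Protocol*

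**What the plan says.** Protocol section 4.2 opens with the blinding claim: "The study will be a double-blind, repeated measures design". Participants are then "randomized on a 1:1:1:1 basis to one of four groups". One of the four is a caffeine-alone arm: "Caffeine (CAF; 3 mg/kg of caffeine + 0.1 g/kg of creatine monohydrate placebo". Section 4.5 analyses the same four arms: "A 4 (group: CR-CAF vs. CR vs. CAF vs. PLA) x 2 (time: pre- vs. post- training".

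Later in section 4.2 the protocol describes an end-of-study question in which "participants will be asked whether they thought they were administered creatine and caffeine, creatine, placebo, or unsure about what supplement they consumed". No other section describes this question or adds to its answers. The protocol does not call it a blinding check, but in a double-blind trial that is its evident purpose.

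**The concern.** The answers do not match the arms. There are four arms, but the answers name three of them plus 'unsure', and the missing one is caffeine alone. This has two consequences if the form follows the sentence.

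- A CAF participant has no answer that correctly identifies his allocation. The recorded rate of correct identification in that arm is zero by construction, however well participants recognise caffeine.
- A participant in any arm who believes he had caffeine alone must choose 'unsure' or give an untrue answer. The design crosses creatine with caffeine, yet caffeine can be reported only together with creatine.

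What is at stake is the evidence for the double-blind claim, because the protocol describes no other participant check of it. Blinding matters here through training effort. Participants "consume the solution 60 minutes prior to exercise", and the sessions are worked to fatigue: "The program will consist of three sets of 6, 8, 10 repetitions to muscle fatigue in order". Someone who recognises caffeine could train differently over the 6 weeks. The route to the outcomes is indirect. Section 4.42 places strength and endurance post-testing 48 hours or more after the final session, and nothing in the protocol calls for a dose before it.

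**Working it through.** **Step 1. Arms against answers.** The arms are from sections 4.2 and 4.5, and the answers from section 4.2.

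| Arm | Active content | Matching answer |
|---|---|---|
| CR-CAF | creatine and caffeine | creatine and caffeine |
| CR | creatine | creatine |
| CAF | caffeine | none |
| PLA | neither | placebo |

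Three of four arms have a match. 'Unsure' is the only other answer and matches no arm.

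**Step 2. The plan's own figure.** Section 4.1 states a required number: the calculation "indicated that 48 participants are required". It is used here only for the arm size. It reproduces with a noncentral F for the group-by-time interaction, using k = 4 groups, m = 2 times, f = 0.25 and alpha = 0.05. The correlation between repeated measures, rho = 0.5, is an assumption because the protocol does not state it.

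- Noncentrality: lambda = f² × N × m / (1 − rho) = 0.0625 × 48 × 2 / 0.5 = 12
- Degrees of freedom: (4 − 1)(2 − 1) = 3 and (48 − 4)(2 − 1) = 44
- Power: 0.803 at N = 48 and 0.760 at N = 44, so 48 is the smallest balanced number that reaches 0.80

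**Step 3. Size of the affected arm.** At equal allocation, 48/4 = 12 participants are in CAF, and 12/48 = 25%.

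**Step 4. Number of correct answers that could be lost in CAF.** Let k now be the number of CAF participants who believe they had caffeine alone. Then 0 ≤ k ≤ 12, and k is the number of lost correct identifications. The remaining 12 − k, who are unsure or believe something else, do have a truthful answer. The documents give no value for k.

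**Step 5. What the CAF row could look like at the extreme, k = 12.** Suppose each of the 12 picks either 'creatine and caffeine' (x of them) or 'unsure' (12 − x).

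| x | Recorded row | Cannot be told apart from |
|---|---|---|
| 12 | 12/12 'creatine and caffeine' | 12 sincere beliefs in the combination |
| 0 | 12/12 'unsure' | 12 participants with no idea |

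Every x from 0 to 12 is possible. The last row is the pattern that intact blinding would give, so complete unblinding to caffeine could look like success. With the missing answer offered, the same 12 participants would show as 12/12 'caffeine only'. Limiting them to two answers is a simplification. An untrue answer could also be 'creatine' or 'placebo', which would make the row harder still to read.

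**The case against.** The strongest reply is that a sentence in a protocol is not the form itself. The exit form is not shown, nothing says the list is closed, and the omission may be a drafting slip with a complete form in use. This stands in part. The loss of data is certain only if the form copies the sentence. But nothing in the document shows a fuller form, and the sentence is wrong against the protocol's own arms in either case.

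A second reply is that little depends on the answer. It is not an endpoint, and the sample size, alpha and ANOVA do not use it. That is correct and limits the weight of the point.

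A third reply is that the feared consequence is measured anyway, because training volume is logged (section 4.3) and compared between groups (section 4.5). That comparison would show a difference in volume but could not say whether it came from expectation or from caffeine. A single guess at the end of the study could not settle this either. The guess does, however, bear directly on whether participants knew what they took, which training volume does not.

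Finally, the figure of 12 is only the arm size and leaves out the other three arms. Both remarks are fair. It is an upper bound on lost correct identifications in CAF, not an expected loss. Beliefs in caffeine alone held in CR-CAF, CR or PLA would add to it, and the documents give no basis for counting them.

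**Conclusion.** The point holds. The answers listed in section 4.2 cover three of four arms. As written, they cannot record a correct identification of CAF, nor a belief in caffeine alone in any arm. The arm concerned has 12 of 48 participants (25%), and between 0 and 12 correct identifications could be lost there. This assumes that allocation is equal, that all 48 participants answer the exit question, and that the form follows the protocol sentence.

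The change should be made, but the point does not threaten the main analysis. Its weight comes from timing: once participants have left without being offered the answer, no later analysis can supply it.

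**What to change.** List the answers in section 4.2 and on the exit form as: creatine and caffeine; creatine only; caffeine only; placebo; unsure. If the form in use already has all five, only the sentence in the protocol needs correcting. Guesses can then be tabulated by arm (4 arms by 5 answers), though the correction does not depend on that.

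The cost is at most one added answer on the form and one corrected sentence. The sponsor should check the form before participants begin to complete the study.
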